The proposed study is designed as a double-blind randomized placebo-controlled trial. Newborn infants born to HIV-negative women from Ilha Josina Maragra or Manhica, Mozambique, an area with stable malaria transmission, will be randomized to one of three cohorts (77 98 infants per cohort). Cohort 1 will receive monthly chemoprophylaxis with sulfadoxine-pyrimethamine (SP) + Artesunate (AS) from 2 until 5 2,5 until 5,5 months of age (doses administered at 2, 3, and 4 2,5; 3,5; 4,5 months) and placebo from 5 to 10 5,5 to 10,5 months of age; Cohort 2 will receive placebo from 2 until 5 2,5 until 5,5 months of age and monthly chemoprophylaxis from 5-10 5,5 to 10,5 months of age (doses administered at 5, 6, 7, 8, and 9 5,5; 6,5; 7,5; 8,5; 9,5 months); and Cohort 3 will receive monthly placebo from 2 to 10 2,5 to 10,5 months of age. We have chosen SP+AS because it was shown to have a 100% clinical efficacy at day 14 of follow up and a parasitological cure of 94% on day 7, without reappearing on day 14, during an antimalarial efficacy trial conducted recently in Manhica [89]. The combination of SP+AS is not currently used in the study area, as the national first line treatment is SP+Amodiaquine (AQ), thus the efficacy of SP+AS is expected to be higher than that of SP+AQ, which has already been used for some time on a wide scale. We have chosen to start SP+AS at 2 months rather than at birth because the use of SP as an anti-malarial is relatively contraindicated in infants less than 2 months of age due to the risk of kernicterus. Furthermore, previous data from our study site indicates that there is essentially no malaria in the first two months

Final protocol: 2nd July 2004 Amendment 1: 15th October 2004 Amendment 2: 2nd December 2004 Amendment 3: 11th July 2005 Amendment 4: 10th August 2005 Amendment 5: 12th September 2006 CONFIDENTIAL

Page 11 of 51

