2- By including Cohort 3, we are attempting to replicate the original observations that led to the formulation of the central [1, 2] – that preventing exposure during the first few months of life (Cohort 1) does not modify the rate at which the infants acquire immunity to malaria as compared to the Control group (Cohort 3). We believe it is necessary to include the Cohort 3 given that we are working in an area of different endemicity from the Tanzanian studies. Cohort 3 is needed in order to measure baseline incidence of parasitemia and clinical malaria episodes and furthermore, it is needed to provide control samples for the immunological assays performed on Cohorts 1 and 2.

Final protocol: 2nd July 2004 Amendment 1: 15th October 2004 Amendment 2: 2nd December 2004 Amendment 3: 11th July 2005 Amendment 4: 10th August 2005 Amendment 5: 12th September 2006

CONFIDENTIAL

CSI/CISM

(Amended 2 December, 2004) (Amended 11 July, 2005)

iv. Case Definition and Detection

Final protocol: 2nd July 2004 Amendment 1: 15th October 2004 Amendment 2: 2nd December 2004 Amendment 3: 11th July 2005 Amendment 4: 10th August 2005 Amendment 5: 12th September 2006 CONFIDENTIAL

Case definition: Any fever upon exam (axillary temperature $\ge 37.5^{\circ}$ C) or history of fever within the prior 24 hours plus the presence of Pf asexual stage parasites of any density will constitute a malaria episode.

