Treatment and follow-up: Any child with uncomplicated malaria will be treated as per standard of care in this area, currently with SP and Amodiaquine, the national first line antimalarial treatment. Children who have severe malaria will be transported by study vehicle to the Manhiça Hospital and referred to the intensive care unit for further care. As per standard of care at the Manhiça Hospital, they will have additional admission labs, including a CBC, glucose, blood culture, and lumbar puncture (if indicated) and will be treated with IV quinine and other support as needed, including intravenous hydration, anti-bacterials, or transfusion. After completing therapy, children will be followed up at routine weekly home visits. Those infants who fail therapy with SP plus Amodiaquine will be treated with a second-line treatment. For those children who have failed second line treatment, treatment will be given with oral quinine. One month after the infection first episode of malaria, the child will have another blood draw for immunological studies. (Amended 11 July, 2005)

v. Study Duration

A child's participation will continue until the child is 25 months of age unless the child is withdrawn, cannot tolerate SP+AS, or the family moves out of the study area. We anticipate a drop-out rate of 15% by the end of the second year and have adjusted our sample size accordingly.

Final protocol: 2nd July 2004 Amendment 1: 15th October 2004 Amendment 2: 2nd December 2004 Amendment 3: 11th July 2005 Amendment 4: 10th August 2005 Amendment 5: 12th September 2006 CONFIDENTIAL

Page 20 of 51

vi. Sample Collection

Field workers will be assigned to conduct the weekly active case detection. They will initially follow the pregnant women and then, upon enrollment of the infants, will be assigned a group of infants from each cohort. In addition, there will be staff available 24 hours a day, 7 days a week at the Ilha Josina *Maragra* Health Center *and Manhiça health center* to evaluate children who present with fever and/or symptoms of malaria. Microscopy and determination of Hematocrit can be performed at the Ilha Josina *Maragra* Health Center. Those samples requiring further work-up will be transported at 4 °C in coordinated transports from Ilha Josina *Maragra* to Manhiça. (Amended 15 October, 2004) (Amended 10 August, 2005)

The timepoints for collection of samples will be:

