(Amended 11 July, 2005) (Amended 10 August, 2005)

viii. Outcome Variables

1. Clinical outcome variables

a) Primary clinical outcome variable

The experience of having at least one episode of clinical malaria in the second year of life *detected by passive case detection.* (Amended 2 December, 2004)

b) Secondary clinical outcome variables

1. Fever (axillary temperature \geq 37.5° C or a history of fever in the previous 24 hours)

2. Hct during first, second and subsequent malaria infections, and during the **24 months** cross-sectional surveys.

3. Density of parasitemia during first, second and subsequent malaria infections, and during the **24** *months* cross-sectional surveys.

4. Time to first clinical episode during the second year of life *detected by passive case detection*.

5. Number of clinical episodes during the first year of life *detected by active or passive case detection*.

6. Number of clinical episodes during the second year of life *detected by passive case detection*. (Amended 2 December, 2004)

2. Immunological outcome variables

a) Primary immunological outcome variables:

 Anti-*Pt*EMP1 antibodies in peripheral blood, as measured at 0, 5, 10, 12, 15, 20 and 25 2.5, 5.5,
10.5, 15 and 24 months of age. The outcome variable to be compared between the cohorts will be: -Antibody units converted from median fluorescence intensity [31]

2. Level-Magnitude and frequency of cytokines (IFN- γ , IL-10) in peripheral blood in response to *in vitro* stimulation with Pf parasite antigens, as measured at 0, 5, 10, 12, 15, 20 and 25 2.5, 5.5, 10.5, 15 and 24 months of age

3. Ratio of Th1 (IFN- γ , TNF α , IL-12 and IL-2) to Th2 (IL-10, IL-5, IL-4) cytokines in plasma, as measured at 0, 5, 10, 12, 15, 20 and 25 **2.5, 5.5, 10.5, 15 and 24** months of age.

4. Anti-GPI antibodies in peripheral blood as measured at 2.5, 5.5, 10.5, 15 and 24 months of age. The outcome variables to be compared between the cohorts will be: -Antibody units converted from ELISA titre -Antibody units converted from Functional Neutralization Assay.

Final protocol: 2nd July 2004 Amendment 1: 15th October 2004 Amendment 2: 2nd December 2004 Amendment 3: 11th July 2005 Amendment 4: 10th August 2005 Amendment 5: 12th September 2006 CONFIDENTIAL

Page 24 of 51

CSI/CISM

5. Host genetics:

-Presence of homozygote or heterozygote for each particular SNP. -Presence or absence of nominated haplotype for each gene.

(Amended 11 July, 2005) (Amended 10 August, 2005)

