b) Secondary immunological outcome variables:

1. Total IgG and IgM IFAT titers against Pf RBC parasite antigens.

2. Ratio of cytophilic-to-non-cytophilic (IgG1+IgG3)/(IgG2+IgG4) IgG isotypes against Pf erythrocytic stage antigens, as measured by IFAT and ELISA.

3. Parasite strains at presentation (determine whether recurrent infections with same parasite strains (implies no/minimal induction of homologous immunity), or new infections with different strains (potential induction of immunity against strains to which the individual has been previously exposed).

4. Ratio of IgM, IgG1, IgG2, IgG3 + IgG4 isotypes against Pf GPI and hemozoin toxins as measured by ELISA.

5. Oxidative stress:

-Quantification of the antioxidant potential measured as enzymatic activity of antioxidant enzymes SOD, catalase and glutathione peroxidase.

-Quantification of the oxidative challenge of the host measured as level of glutathione in RBCs, hemichromes, lipoperoxides and HNE protein adducts in the RBC membrane, thiols, advanced oxidative protein products and HNE protein adducts in plasma.

(Amended 11 July, 2005) (Amended 10 August, 2005)

ix. Sample Size

Population Available: There are approximately 400 infants born yearly in the catchment area of the Ilha Josina at the maternity of the Maragra Health Center. Based on previous experience, we estimate that most mothers will be interested in participating in the study. We expect that less than around 20% of the pregnant women will be HIV-positive and that 25% 20% of the enrolled HIV-negative pregnant women will not enroll their infants due either to drop-out or to birth of an unhealthy or premature infant. We expect a drop-out rate of approximately 15% 20% during the two years each child participates in the study. Infants will be enrolled on a continuous basis as they are born, and enrollment will continue for one year (thus the study will be executed over a three year period). (Amended 15 October, 2004)

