Acute samples: we will define the genotype of the infecting parasite(s) to determine whether infants are susceptible to parasite strains to which they have previously been exposed (presence or absence of strain-specific immunity). *Parasites will be cryopreserved to be used for antibody recognition.* (Amended 10 August, 2005)

Convalescent sample: we will investigate the effect of exposure to Pf erythrocytic antigens on subsequent antibody and cytokine responses evaluated as described above. This will be related to immune responses detected at the time of cross-sectional sampling either side of the clinical episode. The cross-sectional comparison is considered to be the primary immunological outcome but data obtained with the acute and convalescent samples will enhance our capacity to test our hypothesis. (Amended 2 December, 2004)

Final protocol: 2nd July 2004 Amendment 1: 15th October 2004 Amendment 2: 2nd December 2004 Amendment 3: 11th July 2005 Amendment 4: 10th August 2005 Amendment 5: 12th September 2006 CONFIDENTIAL

Page 34 of 51

CSI/CISM

Convalescent sample: we will investigate the effect of exposure to Pf erythrocytic antigens on subsequent antibody and cytokine responses evaluated as described above. This will be related to immune responses detected at the time of cross-sectional sampling either side of the clinical episode.

The cross-sectional comparison is considered to be the primary immunological outcome but data obtained with the acute and convalescent samples after the first episode of malaria will enhance our capacity to test our hypothesis.

(Amended 11 July, 2005)

b) Analysis and interpretation of antibody immunoassays

Primary outcome: Anti-PfEMP1 antibody by flow cytometry in peripheral blood:

The variable outcome measured is:

-Antibody units converted from median fluorescence intensity [31]

Secondary outcomes:

IFA titers against *P. falciparum* infected erythrocytes

Titer log₂(titer/10)+1 with reference to last dilution causing positive fluorescence as compared with non-specific background staining. In addition, we will determine the cytophilic-to-non-cytophilic (IgG1+IgG3)/(IgG2+IgG4) ratio in those plasma samples with detectable IgG antibody levels.

Anti-GPI and anti-hemozoin antibodies by ELISA and FNA in peripheral blood: The outcome variables measured are:

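### A same-strain recurrence soon after treatment is read as absent homologous immunity although it may be an uncleared infection, and the episode definition can count it twice in secondary outcomes

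*Protocol*

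**What the plan says.** Parasite strain at presentation is a secondary immunological outcome (protocol section D.viii, 2.b, item 3). Two readings are offered. Infection with a different strain points to possible immunity against strains met before. The other reading is "recurrent infections with same parasite strains (implies no/minimal induction of homologous immunity". Section D.xi, 2.a repeats this use of genotype on acute samples: "to determine whether infants are susceptible to parasite strains to which they have previously been exposed".

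Section D.iv defines a case as fever, or a history of fever in the preceding 24 hours, "plus the presence of Pf asexual stage parasites of any density will constitute a malaria episode". It sets no minimum interval after a treated episode and no genotype condition. The same section expects some treatment to fail: "Those infants who fail therapy with SP plus Amodiaquine will be treated with a second-line treatment". Section E.1.c names second- and third-line drugs for failures.

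Episodes feed these outcomes in section D.viii, 1.b:
- haematocrit (item 2) and parasite density (item 3) at the first and later infections;
- the first-year episode count by active or passive detection (item 5);
- "Number of clinical episodes during the second year of life", by passive detection (item 6).

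The first-year count is also a candidate predictor in the logistic model for the primary outcome (section D.xi, 1.a). Section D.iii says that the number of parasitaemia episodes will enter the statistical model.

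**The concern.** A parasite of the same genotype found shortly after treatment has at least two explanations. The child may have been re-infected with a strain already met, which bears on homologous immunity. Or the first infection may never have been cleared, which says nothing about resistance to re-infection. The protocol creates the second category by providing for treatment failure, but leaves it out of the interpretation. An uncleared infection would then be reported as failed immunity.

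The same gap affects counting. Under the case definition as written, one infection that is treated, persists and is found again with fever becomes two episodes. That inflates the count outcomes, adds a spurious second infection to the haematocrit and density outcomes, and overstates exposure where the first-year count is used as a covariate.

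**Working it through.** The protocol states no figure on this point, so there is nothing to reproduce. The check compares the relevant sections and then adds an illustration under stated assumptions.

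**1. Is there a rule separating recrudescence from new infection?** None was found: no post-treatment interval, no exclusion from time at risk, no genotype criterion. Incidence is expressed per person-year at risk (section D.ix), but time at risk is not defined. MSP-1/MSP-2 genotyping is planned (section D.x.4) but is not used for this separation.

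**2. Which outcomes are exposed?**
- First-year count (item 5): weekly home visits run to 10.5 months of age, and a smear is taken whenever there is fever or a history of fever (section D.iv, active case detection). A treated child who is febrile at the next visit, about 7 days later, is smeared again. Exposure is direct.
- Haematocrit and density (items 2 and 3): exposed wherever a persisting infection is labelled the second or a later one.
- Second-year count (item 6): detection is passive. The monthly visits from 10.5 to 24 months ask about health status and admissions, with no routine smear described. A failure counts only if the caretaker brings the child back febrile.
- Primary outcome (at least one second-year episode) and time to first second-year episode (item 4): a repeat count in the same child changes neither. The one route is an episode treated just before 12 months that recurs just after.

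**3. What failure rate do the documents give?** None for SP+Amodiaquine, the treatment given to cases. For SP+AS, section C reports "a parasitological cure of 94% on day 7, without reappearing on day 14". It also reports 100% clinical efficacy at day 14, so the remaining 6% is not a symptomatic failure rate. Section C adds that "the efficacy of SP+AS is expected to be higher than that of SP+AQ". The protocol therefore does not expect SP+Amodiaquine to clear every infection, but it gives no usable rate.

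**4. Illustration for counts.** Let f be the share of treated episodes followed by a febrile positive slide from the same infection (assumption: 5-20%). With one possible repeat, counted rate = true rate × (1 + f). If repeats can recur, counted rate = true rate / (1 − f). The true rate is taken as the protocol's 0.4 per person-year (section D.ix).

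| f (assumed) | 0.4 × (1 + f) | 0.4 / (1 − f) |
|---|---|---|
| 5% | 0.42 | 0.42 |
| 10% | 0.44 | 0.44 |
| 20% | 0.48 | 0.50 |

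The single-repeat formula raises counts by 5-20%; allowing repeats takes the upper end to 25% (0.50/0.40).

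**5. Illustration for the primary outcome.** Added probability ≈ rate × (28/365) × f × exp(−rate), taking 28 days as the carry-over period across the 12-month boundary. At rate 0.4:
- 0.4 × 0.0767 × 0.670 = 0.0206;
- × 0.05 = 0.0010 and × 0.20 = 0.0041.

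That is about 0.1 to 0.4 percentage points. It is on the high side, because it lets every failure of an episode in those 28 days fall after the boundary and be detected.

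**The case against.** The strongest reply is that section D.iv is a diagnostic definition, not a counting algorithm, and that intervals between episodes and exclusions from time at risk usually belong in the SAP. This carries weight for the counting half: the interval could properly sit there, and the protocol nowhere says that a failure is logged as a new episode. It does not answer the strain half. The reading of a same-strain recurrence is stated outright and is invalid for early recurrences whatever an SAP adds.

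Four stronger readings are tempting, and the documents do not support them.
- A reader might infer that the primary comparison is compromised. It is binary, and the boundary effect is under half a percentage point on the assumptions above.
- A reader might infer that repeated SP prophylaxis selects resistant parasites, so that failures cluster in Cohorts 1 and 2 and mimic rebound. This is a possibility only. No cohort-specific failure rate is given, and the last active doses are at 4.5 and 9.5 months, before the second year starts. Even an assumed 10% against 20% turns a true rate ratio of 1.00 into 1.20/1.10 = 1.09, against a hypothesised relative risk of at least 2.0.
- A reader might infer that the second-year count is inflated as much as the first. Weekly visits have ended by then, so it is not exposed in the same way.
- A reader might infer that every early same-genotype recurrence is a treatment failure. Re-infection with a common MSP-1/MSP-2 type is possible, so genotype alone proves neither reading.

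It is also fair to say that the documents do not supply a 28-day window. Section A presumes about one month of suppression per SP dose, so a suppressed infection could resurface after day 28. That is a reason to test a longer window, not to have none.

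**Conclusion.** The point holds with limited scope. The homologous-immunity reading is wrong as a general rule, because it leaves out the uncleared infections that the protocol itself anticipates. Read literally, the case definition also allows a double count. That matters mainly for the first-year count and its use as a covariate, and for haematocrit and density at second and later infections; it matters less for the second-year count. The primary outcome and time to first episode are essentially unaffected.

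The true size cannot be obtained from the documents. The 5-20% range for f is an assumption, as is equal failure across cohorts. This should be corrected, but it does not threaten the main conclusion of the trial.

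**What to change.** **Count, haematocrit and density outcomes (D.viii, 1.b, items 2, 3, 5 and 6):** state that a positive febrile slide within a pre-specified window after treatment of an episode belongs to that episode. Use 28 days, for example, with a sensitivity analysis using a longer window. Remove the window from time at risk. Use the same count wherever the number of first-year episodes enters a model.

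**Strain outcome (D.viii, 2.b, item 3, and the acute-sample text in D.xi, 2.a):** base the homologous-immunity reading only on recurrences after the window. Report same-genotype recurrences inside it separately by cohort as possible recrudescence, and withdraw the present interpretation for them.

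The counting rule may sit in the SAP; the interpretive sentence should be corrected in the protocol. These are analysis and labelling rules that leave treatment unchanged and use dates and genotypes already due to be collected. The cost is that a few genuine early re-infections are not counted.

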The three cohorts are proposed in order to address the **central hypothesis**: Exposure to Pf erythrocytic stage antigens in early infancy does not contribute to the development of naturally acquired immunity to malaria but exposure after 5 months of age does contribute to the development of naturally acquired immunity. Specifically, the three cohorts are needed to address the following:

1- The comparison of Cohort 1 (prophylaxis 2-5 2,5-5,5 months) and Cohort 2 (prophylaxis 5-10

5,5-10,5 months) is the key comparison. During the first 10 months of life, we assume that both Cohorts 1 and 2 will have experienced exposure to Pf blood stage parasites, and therefore Pf erythrocytic stage antigens, since each have been left unprotected by prophylaxis during several months. We recognize that infants in the first 5 months of life are likely to have a greater degree of protection due to maternal antibodies than those who are 5-10 months of age, although there is some controversy with regard to this [72]. Nevertheless, previous data from our study site indicate that there is essentially no malaria in the first two months of life but that after 2 months, the age-specific incidence of clinical episodes of malaria increases to levels near that of the second year of life. We also recognize that younger infants may be kept more covered by their mothers and thus experience less exposure to mosquitoes. Thus, the rate of malaria acquisition in the two cohorts may not be the same. Because this will be an uncontrolled variable that may affect the outcome measures of the

Final protocol: 2nd July 2004 Amendment 1: 15th October 2004 Amendment 2: 2nd December 2004 Amendment 3: 11th July 2005 Amendment 4: 10th August 2005 Amendment 5: 12th September 2006 CONFIDENTIAL

Page 17 of 51

[figure not shown]
study, the effects of the number of episodes of parasitemia will be included in the statistical model used for analysis (see below). (Amended 2 December, 2004)

[figure not shown]

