Sample size calculations: All sample size calculations are based on $\alpha = 0.05$ (two-tailed) and B = 0.20. With **n** = **65 78** per cohort, we have 80% power (using a two-tailed test) to detect a relative risk of 2 in Cohort 2 as compared to Cohort 1 for at least one clinical malaria episode in the second year of life and to detect of relative risk of 2 in Cohort 2 as compared to Cohort 3, *assuming an incidence of clinical malaria of 0.4 episodes per person-year at risk*. Because *a priori* we intend to make 3 comparisons (Cohort 1 to Cohort 2, Cohort 1 to Cohort 3, and Cohort 2 to Cohort 3), adjustment of the

Final protocol: 2nd July 2004 Amendment 1: 15th October 2004 Amendment 2: 2nd December 2004 Amendment 3: 11th July 2005 Amendment 4: 10th August 2005 Amendment 5: 12th September 2006 CONFIDENTIAL

Page 25 of 51

p value using the Dunn-Sidak method is necessary. Thus, we consider significant a p-value lower than 0.017. We expect to see similar risks between C1 and C3. We will have 80% power to determine that the relative risk is not greater than 2 between the Cohorts 1 and 3. However, detecting a smaller difference would require much larger sample sizes (i.e. 2074 2413 per cohort to detect a difference of 15%) and is not practical for the purposes of this study. (Amended 15 October, 2004)

We anticipate a 15% 20% loss to follow-up and thus our sample size will be increased accordingly to n = 77 98 per cohort. We will first enroll all infants aged 0-2 months from the Maragra area who are eligible for the study and whose mothers have signed an informed consent. We will then start recruiting pregnant women and enrolling their eligible infants as they are born. The number of pregnant women to be enrolled will depend on the number of infants 0-2 months of age recluted in the community. Because we expect that approximately 25% 20% of the pregnant women initially enrolled will not ultimately be included in the study (due to drop-out or delivery of a baby who is not full-term and healthy) we will enroll 103 122 HIV-negative mothers per cohort or a total of 309 366 increase the number of HIV-negative pregnant women to be enrolled accordingly. Given that our previous data indicates that there are at least 400 births per year in Ilha Josina Maragra, we anticipate no problems in enrolling the required number of volunteers over a one year period. (Amended 15 October, 2004) (Amended 2 December, 2004)

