The primary aim of the study is to determine the effect of timing of exposure to Pf erythrocytic stage antigens during infancy (0 to 5 vs 5 to 10 months of age) on subsequent morbidity due to clinical malaria. The primary outcome variable was chosen as the presence or absence of at least one episode of clinical malaria during the second year of life **as detected by passive case detection**, because current epidemiological data suggests that this outcome is a sensitive, inverse indicator of NAI; when used as the primary outcome variable in studies detailed earlier in this proposal (see background and rationale sections) significant differences were detected between cohorts receiving differing prophylaxis [1, 2]. In the study site, an incidence of **0.4 0.48**-episodes of clinical malaria per person year at risk ([name], personal communication). Thus, as described in the sample size section, each of the three cohorts will be compared to the others in pairwise fashion, with the p value for significance reduced to 0.017 to adjust for the three comparisons. **(Amended 15 October, 2004) (Amended 2 December, 2004)**

However, other variables could also affect the likelihood of experiencing at least one clinical episode during the second year of life, such as number of clinical episodes experienced during the first year of life, regardless of the age at which they occurred. In addition, we believe that immunological responses during the first year of life may potentially explain the differences in susceptibility to clinical episodes during the second year (secondary aim), although other factors, such as host genotype (e.g., presence or absence of sickle cell trait, α -thalassemia or others), the presence of haemoglobin AF, parasite genotype, and possibly maternal immune responses, could also affect the primary outcome variable. Because we do not know which of these many factors will be most closely associated with the outcome, we propose a logistic regression analysis to make this assessment. All of these factors will be used in a multiple logistic regression model, and those with significant associations will be identified. Although it is by no means assured, we hope that one of the immunological measurements (see below) will show a significant association and thus will serve as a positive or negative correlate with NAI. A rationale has been provided regarding the concentration of antibody responses to PfEMP-1 as a likely candidate.

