Final protocol: 2nd July 2004 Amendment 1: 15th October 2004 Amendment 2: 2nd December 2004 Amendment 3: 11th July 2005 Amendment 4: 10th August 2005 Amendment 5: 12th September 2006 CONFIDENTIAL

Page 32 of 51

A similar logistic analysis will be conducted with a second important clinical outcome: whether or not each participant experiences a Hct < 25% during the second year of life, as measured during the $\frac{12}{15}$, $\frac{15}{20}$ and $\frac{25}{24}$ month cross-sectional surveys. Although it is perhaps less clear how the immunological responses we are measuring might impact on Hct, it is nevertheless a primary indicator of morbidity and also a primary target for interventions such as anti-morbidity malaria vaccines or prophylaxis regimens, and is proposed here as a secondary outcome. (Amended 2 December, 2004)

b) Overall Interpretation of Results

Our prediction: We hypothesize that the relative risk of having at least one clinical episode of malaria in the second year of life will be 2.0 or greater in Cohort 2 as compared to Cohort 1 and 3. If this is true, it will support our hypothesis that the infant immune system is able to mount protective responses provided that exposure occurs following month 5, but cannot do so if exposure occurs earlier but is absent between months 5 to 10. This finding would have important implications for future vaccine trials, for which the timing of administration of malaria vaccines would then be judged to be critical if they are to induce protection against blood stage infection.

Another expected finding of this study is that Cohort 1, and to a lesser extent Cohort 2, will have reduced frequencies of parasitemia and clinical episodes of malaria during the first year of life, due to the protective effects of SP + AS administration. A key strategy for public health planners is how to achieve this protective effect without causing a rebound parasitemia during the second year of life. Ultimately, it may be important to repeat studies such as this in several geographic locations, in order to assess how a variety of transmission intensities, parasite genotype frequencies, host populations, vector populations, etc., may influence the relationship between the administration of prophylaxis, in particular its intensity and timing, and lasting gains in child health.

c) Additional Analyses of Clinical and Parasitological Data: Cross sectional and Prospective.

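### A flat 0.017 for all three cohort comparisons is valid but inefficient; a three-group step-down keeps familywise error at about 5% and never rejects less

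*Protocol*

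**What the plan says.** Section D.ix (Sample Size) sets the overall error rates, "0.05$ (two-tailed) and B = 0.20", and announces the tests in advance: "we intend to make 3 comparisons (Cohort 1 to Cohort 2, Cohort 1 to Cohort 3, and Cohort 2 to Cohort 3". It then fixes the threshold: "p value using the Dunn-Sidak method is necessary. Thus, we consider significant a p-value lower than 0.017".

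Section D.xi.1.a (Overall Analytical Plan) repeats the rule for the primary outcome: each cohort is compared with the others in pairs, "with the p value for significance reduced to 0.017 to adjust for the three comparisons". No step-down, gate or order is given for these three tests.

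The comparisons do not carry equal weight. Section D.iii (Rationale for the 3 cohorts) says of Cohort 1 versus Cohort 2: "5,5-10,5 months) is the key comparison". Section D.xi.1.b (Overall Interpretation of Results) predicts that the relative risk "will be 2.0 or greater in Cohort 2 as compared to Cohort 1 and 3". Section D.ix expects Cohorts 1 and 3 to have similar risks.

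Power is stated pair by pair: 80%, two-sided, for a doubled risk in Cohort 2, first with Cohort 1 and then with Cohort 3 as the comparator. The baseline is given as "assuming an incidence of clinical malaria of 0.4 episodes per person-year at risk". No power is stated for showing both differences together.

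**The concern.** The central prediction needs two rejections, Cohort 2 against Cohort 1 and Cohort 2 against Cohort 3. Under a single-step rule each must pass 0.017 whatever the other shows.

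That is stricter than familywise control requires here. Among three groups the pairwise null hypotheses are linked: two of them cannot hold without the third. So once one pair differs, at most one true null is left and a test of it at 0.05 is enough.

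What is at stake is power. Section D.ix records that Amendment 5 raised the total to 350 because first-year incidence was below expectation. A sharper decision rule adds power without more infants or blood draws.

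**Working it through.** **Inputs from the protocol.** Two-sided 0.05 overall, 0.017 per pair, 80% power; incidence 0.4 per person-year, doubled in Cohort 2; 78 evaluable per cohort; 20% loss; total 350; allocation 1:1:1; binary outcome (at least one episode in the second year of life).

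**Assumptions.** Cohorts 1 and 3 have equal risk. Evaluable n after Amendment 5 is 350/3 × 0.8 = 93. Incidence of 0.2 or 0.3 stands in for lower than expected, since the protocol gives no figure. Risk from a rate is 1 − exp(−rate).

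**1. The threshold.** 1 − 0.95^(1/3) = 0.01695, so 0.017 is right.

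**2. The sample size.** The two-rate formula n = (z₁ + z₂)² (λ₁ + λ₂)/(λ₁ − λ₂)², with z₁ = 2.387 (two-sided 0.017), z₂ = 0.842, λ = 0.4 and 0.8, gives 10.42 × 1.2/0.16 = 78.2. The stated 78 reproduces and already carries the 0.017. The same formula with the superseded 0.48 gives 65.1, matching the superseded 65.

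**3. Why the step-down is valid.** Write H12, H13 and H23 for the pairwise nulls. Any two together imply the third, so every intersection of two is the global null. A closed test therefore needs only two steps: the global null must be rejected (smallest p below 0.017), then each pair is tested at 0.05. A pair below 0.017 passes both steps, so every rejection under the current rule is kept.

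**4. Joint power at the protocol's own rate inputs** (0.4 versus 0.8 on person-time, n = 78): 70.0% under the current rule, 82.6% under the step-down, a gain of 12.6 points. The gain is 9.2 at n = 93 and 5.3 at n = 116.

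**5. Binary outcome.** Simulation of three cohorts, pooled z-tests, 400,000 trials per row. Each cell is current rule → step-down, in %. Full pattern means both Cohort 2 differences and no Cohort 1 versus 3 difference.

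| Cohorts 1 and 3 vs Cohort 2 | n | Both C2 comparisons | C2 vs C1 alone | Full pattern |
|---|---|---|---|---|
| Rate 0.4 vs 0.8 (risk 0.33 vs 0.55) | 78 | 53.1 → 65.5 | 67.6 → 73.8 | 52.8 → 63.8 |
| same | 93 | 60.5 → 75.0 | 73.9 → 81.2 | 60.1 → 72.6 |
| Rate 0.3 vs 0.6 (risk 0.26 vs 0.45) | 78 | 38.5 → 54.8 | 55.1 → 63.2 | 38.4 → 53.5 |
| same | 93 | 49.4 → 64.9 | 64.4 → 72.1 | 49.2 → 63.1 |
| Rate 0.2 vs 0.4 (risk 0.18 vs 0.33) | 93 | 31.1 → 46.4 | 47.6 → 55.3 | 30.9 → 45.4 |
| Risk 0.20 vs 0.40 | 93 | 59.4 → 74.3 | 73.0 → 80.4 | 59.0 → 71.9 |
| Risk 0.26 vs 0.52 | 93 | 83.9 → 91.9 | 90.4 → 94.4 | 83.0 → 88.1 |
| Risk 0.33 vs 0.66 | 78 | 94.6 → 97.4 | 97.0 → 98.4 | 93.4 → 92.8 |
| same | 93 | 97.3 → 99.1 | 98.5 → 99.5 | 95.9 → 94.2 |

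At risk 0.26 versus 0.52 with n = 78, joint power goes from 74.7% to 85.5%, about 11 points.

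**6. Error rates.** With all cohorts equal (risk 0.33), the chance of any false rejection is 4.4 to 4.5% under either rule. With Cohorts 1 and 3 equal and Cohort 2 different, the only possible false rejection is Cohort 1 versus 3: about 1.7% under the current rule and 4.6 to 5.2% under the step-down.

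**7. Plain Holm.** At rate 0.4 versus 0.8 and n = 78, joint power is 59.8%, a gain of about 7 points rather than 12. Holm does not use the link between the three nulls.

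**The case against.** The strongest reply is that nothing here is an error. The protocol names its comparisons, uses a recognised method, computes the threshold correctly and applies it in both sections; its sample size already pays for the adjustment. That stands. A reader might infer that the threshold is wrong, or that the stated 80% per-pair power ignores the adjustment; the documents support neither.

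A second reply concerns size. Section D.ix speaks of a relative risk of 2 for at least one episode. If the risk itself doubles from the 0.33 implied by an incidence of 0.4, joint power is already 95 to 97% and the gain is 2 to 3 points. The larger gains come from doubling the rate, which gives a risk ratio of 0.55/0.33 = 1.67, or from a lower baseline risk. That stands too. The sample size of 78 does come from a rate formula, so the rate reading is a fair one, but a gain of 12 points or more cannot be quoted as general.

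A third reply concerns Cohort 1 versus Cohort 3. It is tempting to call the step-down free of extra false positives and the alpha spent on this pair wasted. Neither is right. Similarity of these cohorts is part of the central hypothesis, and a false difference between them becomes about three times as likely when Cohort 2 truly differs. It stays within the familywise limit. In the low-power scenarios the full predicted pattern still becomes more likely; where power is already very high it becomes slightly less likely, by about 0.5 to 2 points.

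Dropping the Cohort 1 versus 3 test and running the other two in fixed order would remove a pre-specified comparison. That is a trade-off, and it is not recommended here.

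**Conclusion.** The single-step 0.017 is valid and conservative; the finding is lost efficiency. A three-group step-down gives the same familywise guarantee and never rejects less.

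The size depends on what doubling means and on the baseline. Joint power rises by about 12 to 16 points in the scenarios where the rate doubles from 0.2 to 0.4 per year or risk goes from 0.20 to 0.40, at n = 78 to 93. It rises by about 2 to 8 points at n = 93 when risk doubles from 0.33 or 0.26. The named key comparison alone gains about 6 to 8 points in the first group and 1 to 4 in the second.

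These figures assume equal risk in Cohorts 1 and 3 and 20% loss; the incidences of 0.2 and 0.3 are assumed. The lower-incidence scenarios are the relevant ones if the shortfall reported with Amendment 5 carries into the second year of life, which the protocol does not establish.

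**What to change.** Before unblinding, replace the flat threshold in sections D.ix and D.xi.1.a with one rule worded alike in both: the smallest of the three pairwise p-values must be below 0.017; if it is, each of the other two pairs is tested at 0.05; if not, no pair is declared different. Name it as a closed (Shaffer-type) step-down for three groups, so that it is not read as plain Holm.

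Add that familywise error stays at about 5% and that, if Cohort 2 truly differs, a false Cohort 1 versus 3 difference has a chance of about 5% instead of 1.7%. All three planned comparisons stay.

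The cost is a sentence or two of text. Sample size, visits and data collection do not change.
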